#### 8 STATISTICAL METHODS

Prior to the database lock, a detailed, finalized Statistical Analysis Plan will be completed and placed on file. The Statistical Analysis Plan will contain a more comprehensive explanation than that provided here of the methodology used in the statistical analyses, as well as the rules and data handling conventions used to perform the analyses and the procedure used to account for missing data. Data will be summarized overall and also broken down by the treatment arm.

#### 8.1 Analysis Populations

Safety and efficacy results will be summarized descriptively for all subjects who receive treatment in this study.

#### 8.2 Efficacy Analysis

Compare subject pain scores (VAS) between PN40082 and RV001 with topical anesthetic and RV001. Change from baseline will be summarized for LFGS and POL. Other efficacy variables include pGAI, iGAI, and Swelling Assessment at Visit 2/Month 1.

#### 8.3 Safety Analysis

Adverse events will be coded to system organ class and preferred terms using the Medical Dictionary for Regulatory Activities (MedDRA, Version 20 or higher).

Frequency and percentage of subjects reporting TEAEs will be tabulated overall and for each treatment in PRO 2019-02 by preferred terms and further by severity and relationship to study device. In summaries of severity and relationship, subjects reporting more than one event in a treatment arm that are mapped to the same preferred term will be counted only once in that treatment arm under the strongest severity and relationship, respectively. In addition, visual related TEAEs will be summarized separately by preferred term.

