## **Safety Analysis:**

Safety of the treatment with PN40082 or RV001 with topical anesthetic or RV001 will be evaluated by the nature, severity, and frequency of treatment-emergent adverse events (TEAEs). All AEs that occur during the study will be recorded whether or not they are considered to be related to treatment. A description of the AE will be recorded with the date of onset, date of resolution, severity of the AE, relationship to the study device, action taken, and the outcome. The frequency and type of AEs will be evaluated for each group based on the previous treatments that they received in the PRO 2018-02 and PRO 2018-03 protocols, and the difference in AEs in this protocol (PRO 2019-02) between the subjects who received injections that contained lidocaine, and the group that was treated with topical lidocaine. Safety of repeat injections, comparing incidence of reported AEs from all three studies, PRO 2018-02, PRO 2018-03, and PRO 2019-02 will be discussed in the clinical study report. Adverse events will be coded to system organ class and preferred terms using the Medical Dictionary for Regulatory Activities (MedDRA, Version 20 or higher).

Frequency and percentage of subjects reporting treatment-emergent adverse events (TEAEs) will be tabulated overall and for each treatment in PRO 2019-02 by preferred terms and further by severity and relationship to study device. In summaries of severity and relationship, subjects reporting more than one event in a treatment arm that are mapped to the same

preferred term will be counted only once in that treatment arm under the strongest severity and relationship, respectively. In addition, visual-related TEAEs will be summarized separately by preferred term.

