## 7.2 Beginning and End of Study

A subject is considered to be enrolled in the study when he/she has provided written informed consent.

A subject is considered to have completed the study after he/she has completed the Day 168 Month 6/End of study telephone call.

A subject is considered to have withdrawn after he/she has withdrawn consent or has been withdrawn under the conditions specified in Section 7.3.3.

A subject is considered to have been lost to follow-up if he/she cannot be contacted by the investigator. The investigator will document efforts to attempt to reach the subject at least twice by telephone and will send a certified letter before considering the subject lost to follow-up. The end of participation for a subject lost to follow-up is documented as the date of the certified letter.

Each subject will be monitored for the occurrence of AEs, including serious adverse events (SAEs), starting immediately after treatment initiation. Each subject will be followed for safety monitoring until he/she is discharged from the study.

Follow-up procedures related to pregnancy, AEs, or SAEs may continue beyond the end of the study.

Each subject will participate in the study for approximately 6 months from the time he/she signs the ICF through the final contact. After determination of eligibility at Visit 1/Day 1, each subject will be treated with study device.

It is anticipated that the duration of this study will be 20 months from the beginning to the end of the study (first subject signing the ICF to last contact with last subject).

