## 7.9 Assessment of Safety

## 7.9.1 Safety Endpoints

Safety of the treatment with PN40082 or RV001 with topical anesthetic, or RV001 will be evaluated by the nature, severity, and frequency of treatment-emergent adverse events (TEAEs). All AEs that occur during the study will be recorded whether or not they are considered to be related to treatment. A description of the AE will be recorded with the date of onset, date of resolution, severity of the AE, relationship to the study device, action taken, and the outcome. The frequency and type of AEs will be evaluated for each group based on the previous

treatments that they received in the PRO 2018-02 and PRO 2018-03 protocols, and the difference in AEs in this protocol (PRO 2019-02) between the subjects who received injections that contained lidocaine, and the group that was treated with topical lidocaine.

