#### WARNINGS

- Defer use of *PN40082* at specific sites in which an active inflammatory process (skin eruptions such as cysts, pimples, rashes, or hives) or infection is present until the process has been controlled.
- Injection site reactions (e.g., lip swelling, lip pain, and contusion) to *PN40082*, including short-term minor or moderate inflammatory symptoms starting shortly after treatment of lips
- PN40082 must not be implanted into blood vessels. Localized superficial necrosis and scarring may occur after injection in or near vessels, such as in the lips, nose, or glabellar area. It is thought to result from the injury, obstruction, or compromise of blood vessels.
- Delayed onset inflammatory papules have been reported following the use of dermal fillers. Inflammatory papules that may occur rarely should be considered and treated as a soft tissue infection.

- Injections of 4.0 mL or greater (upper and lower lip combined) per treatment session increases the occurrence of injection site reactions. If a volume of more than 3 mL is needed to achieve optimal correction, a follow-up treatment session is recommended.
- As with all dermal filler procedures, PN40082 should not be used in vascular rich areas.
   Use of similar products in these areas, such as glabella and nose, has resulted in cases of vascular embolization and symptoms consistent with ocular vessel occlusion, such as blindness.

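### The planned TEAE tables carry no onset time: they cannot show which events were late, and a late repeat of a preferred term adds nothing to its incidence

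*Combined protocol and SAP*

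**What the plan says.** Section 8.3 defines the main table: "Frequency and percentage of subjects reporting TEAEs will be tabulated overall and for each treatment in PRO 2019-02 by preferred terms". It is then split by severity and by relationship to the device. For those two splits, "subjects reporting more than one event in a treatment arm that are mapped to the same preferred term will be counted only once", and the one entry kept is placed "in that treatment arm under the strongest severity and relationship, respectively". The synopsis (Safety Analysis) repeats the rule. The only other TEAE table specified in Section 8.3 is a separate preferred-term summary of visual events.

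Section 7.2 has AE monitoring "starting immediately after treatment initiation" and continuing until discharge; completion is the Day 168 call. Section 7.9.1 shows that timing is collected: "A description of the AE will be recorded with the date of onset, date of resolution, severity of the AE". Section 7.9.1 and the synopsis add comparisons by previous treatment and by lidocaine route, and the synopsis adds a comparison across the three studies. None of these uses onset time or duration.

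The Warnings in Appendices 2 and 3 describe short-term inflammatory symptoms that begin soon after treatment and, as a separate item: "Delayed onset inflammatory papules have been reported following the use of dermal fillers".

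**The concern.** Safety of repeat injection is a stated objective (Section 6), and the documents themselves recognise both an early and a delayed type of reaction. After Visit 2 the scheduled contacts are two telephone calls, Day 56 and Day 168, both of which assess AEs. No table described in the protocol shows separately what that part of follow-up yields.

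Two consequences follow.

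- Every late event enters the tables without its timing, so a reader cannot separate it from an expected early reaction.
- If a subject has an early event and later a new event coded to the same term, the late one does not change the incidence. It alters the severity or relationship table only if it is the stronger of the two, and then without any sign that it was late.

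A difference between arms in late reactions could therefore be diluted in the single-period table.

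**Working it through.** The documents contain no AE rate, power statement or target difference on this point, so there is no plan figure to reproduce. The check has two parts.

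**1. Is there a split by onset anywhere?** I compared the synopsis (Safety Analysis) and Sections 7.9.1, 7.9.2, 7.9.3.4, 8, 8.1 and 8.3. Onset and resolution dates are recorded for each AE. Time to onset is otherwise required only in individual AESI reports (Section 7.9.3.4), which cover visual, embolic and ischemic events. No table by onset window, no event count and no duration summary is described. No TEAE window is defined either, so I take the period to be AE collection itself: treatment to the Day 168 call.

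**2. How much could a single-period count hide?** Inputs:

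- Number of subjects: anticipated to be below 158 (synopsis, Number of Subjects). Allocation is 1:1:1 (Section 7.4.2). 158/3 = 52.7, so I use 52 per arm as an upper figure.
- Assumed, not in the documents: early rate of a given term pe = 30%, 60% or 90%; late rate of the same term pl = 5% (range 2% to 10%); independence within subject.

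Formulas:

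- Once-per-subject incidence = 1 − (1 − pe)(1 − pl)
- Rise caused by late events = pl(1 − pe)
- Share of late events that add nothing = P(early given late), which equals pe under independence

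With pl = 5%, the expected number of subjects with a late event is 52 × 0.05 = 2.6 per arm.

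| pe | Incidence in the single table | Rise due to late events | Late cases that add nothing (of 2.6) |
|---|---|---|---|
| 30% | 1 − 0.70 × 0.95 = 33.5% | 3.5 points | 2.6 × 0.3 = 0.8 |
| 60% | 1 − 0.40 × 0.95 = 62.0% | 2.0 points | 2.6 × 0.6 = 1.6 |
| 90% | 1 − 0.10 × 0.95 = 90.5% | 0.5 points | 2.6 × 0.9 = 2.3 |

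At the same three early rates, the rise is 1.4, 0.8 and 0.2 points for pl = 2%, and 7.0, 4.0 and 1.0 points for pl = 10%.

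For a contrast between arms, suppose the early rate is equal and the late rate is 2% against 10%, a late difference of 8 points. The single table shows 8 × (1 − pe) = 5.6, 3.2 or 0.8 points. A table by onset window would show all 8.

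Independence matters. If subjects who react early are also more likely to react late, the share that adds nothing exceeds pe; if they are less likely, it is smaller.

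**The case against.** A reader might infer that a delayed reaction disappears, or that the counting rule is an error. The documents do not support either reading.

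- Once-per-subject incidence is the usual safety summary. The explicit count-once sentence is limited to the severity and relationship breakdowns and keeps the strongest event, so a worse late event does supply the grade. The main table has the same effect on repeats only because it counts subjects.
- Nothing is lost from the data. Each AE is recorded with its dates, and listings or further tables can be made from them.
- The delayed harm that the Instructions for Use name is papules. These would normally be coded to their own term and counted, unless the subject already had that term. For them the gap is only missing timing. A recurrent late swelling under an already used term is a plausible case, but no section describes one.
- Section 8 defers methods and data-handling rules to a separate SAP, whose text is not included in the document reviewed. It may already contain an onset split.
- The rates used above are assumptions. Section 7.9.8 leaves it to the investigator whether diary events persisting past the last diary day become AEs. If few early events are recorded as AEs, less is masked.
- AESI reports carry time to onset, visual TEAEs have their own table, and repeat-injection safety is also addressed by the comparison across studies.

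All of this stands, and it limits the point to how events are tabulated. It does not supply timing for non-AESI events in any table the protocol describes, and nothing in the protocol commits the SAP to provide it.

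**Conclusion.** This is a worthwhile and cheap improvement, not an error in the plan. As described, the TEAE tables cannot show which events were late, and a late event under a term the same subject already had adds nothing to the incidence. A late event under a new term, or in a subject without the early term, is counted but untimed.

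The size is unknown because the documents give no rates. The general result is that the masked share of late same-term events equals the early rate of that term. This rests on independence and on TEAEs being counted over the whole period to Day 168. The case counts also rest on about 52 subjects per arm, which is an upper figure. The point concerns tabulation only and has no bearing on clinical management.

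**What to change.** Keep the overall table. In Section 8.3, the synopsis and the SAP, add:

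- TEAEs by arm, preferred term and onset window, for example Day 1–14, Day 15 to Visit 2, and after Visit 2 to the Day 168 call;
- the once-per-subject rule applied within each window, so that a late recurrence counts in its own window;
- event counts beside subject counts, with a new onset after documented resolution counted as a new event;
- duration (resolution date minus onset date) for injection-site terms.

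Before fixing the first boundary, reconcile the diary text. Section 7.6.25 describes a two-week diary collected at Visit 2, while Section 7.9.5 also mentions one dispensed at Visit 2 for the rest of the study.

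The cost is a few extra descriptive tables from dates already recorded, with no new data or visits. Cells will be small: under the illustration, a 5% late rate gives about 2.6 subjects per arm. The tables should therefore be read descriptively, in line with Section 8.1.

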#### 8.4 Sample Size Determination

The maximum sample size was determined by the number of subjects who competed Protocol PRO 2018-02 and the number of subjects who rolled over into PRO 2018-03.

#### 9 ETHICS

#### 9.1 Informed Consent

The principles of informed consent, according to Food and Drug Administration (FDA) regulations and International Council for Harmonization (ICH) guidelines on Good Clinical Practice (GCP), will be followed. A copy of the proposed ICF must be submitted with the protocol to the IRB for approval.

The informed consent process must be conducted and the ICF must be signed before each subject undergoes any Visit 1 procedures that are performed solely for the purpose of determining eligibility for the study, in compliance with 21 CFR Part 50. Each subject's signed ICF must be kept on file by the investigator for inspection by regulatory authorities at any time. A copy of the signed ICF will be given to the subject. A notation will be made in the subject's medical record indicating the date and time informed consent was obtained.

## 9.2 Institutional Review Board (IRB)

The study protocol and ICF must be approved in writing by an appropriate IRB as defined by FDA regulations and other applicable requirements prior to enrollment of any study subjects.

Any changes to the protocol or a change of investigator approved by the Sponsor must also be approved by the site's IRB and documentation of that approval provided to the Sponsor or designee. Records of the IRB review and approval of all documents pertaining to this study must be kept on file by the investigator and are subject to inspection by regulatory authorities during or after completion of the study. SAEs must also be reported to the IRB.

Periodic status reports must be submitted to the IRB at least annually, as well as notification of completion of the study and a final report within 1 month of study completion or termination. A copy of all reports submitted to the IRB must be sent to the Sponsor or designee.

The investigator will ensure that an IRB that complies with the requirements set forth in 21 CFR Part 56 will be responsible for the initial and continuing review and approval of the study.

#### 9.3 Subject Confidentiality

All subject data will be identified only by a subject identification number and subject initials. However, in compliance with federal guidelines regarding the monitoring of clinical studies and in fulfillment of his/her obligations to the Sponsor, the investigator must permit the study monitor, Sponsor representative or auditor, and/or FDA representative or other regulatory

authority to review the portion of the subject's medical record that is directly related to the study. This shall include all study-relevant documentation including medical history to verify eligibility, admission/discharge summaries for hospital stays occurring while the subject is enrolled in the study, and autopsy reports if a death occurs during the study.

As part of the required content of informed consent, each subject must be informed that his or her medical chart may be reviewed by the Sponsor, the Sponsor's authorized representatives, FDA or other regulatory authority. If access to the medical record requires a separate waiver or authorization, it is the investigator's responsibility to obtain such permission from the subject in writing before the subject is entered into the study.

## 9.4 Study Registration

The study will be registered by the Sponsor on an appropriate free public website such as clinicaltrials.gov, which is a service of the United States National Institutes of Health.

#### 10 DATA HANDLING AND RECORDKEEPING

#### 10.1 Site Regulatory Documents Required for Initiation

The Sponsor or designee will receive the following documents prior to the initiation of the study:

- Completed, signed Form FDA 1572
- Current curricula vitae, signed and dated, for the PI and co-investigators named on Form FDA 1572
- Current license(s) of the PI and co-investigators named on Form FDA 1572
- Documentation of IRB approval of the study protocol, investigator, and ICF
- Current IRB membership list
- A copy of the protocol signature page signed by the PI
- Original Non-disclosure Agreements for the PI and co-investigators named on Form FDA 1572
- Debarment Certification for the PI and co-investigators named on Form FDA 1572
- Financial Disclosure Statement for all individuals named on Form FDA 1572

#### 10.2 Maintenance and Retention of Records

The study will be conducted according to GCP as outlined in ICH guidelines by the FDA. It is the responsibility of the investigator to maintain a comprehensive and centralized filing system of all relevant documentation. Investigators will be instructed to retain all study records required by the Sponsor and the regulations in a secure and safe facility with limited access. Regulations require retention for a period of at least 2 years after marketing approval and notification from the Sponsor. These regulatory documents should be retained for a longer period if required by local regulatory authorities.

These records include documents pertaining to the receipt and return of study device, IRB, informed consent, source documents, and final signed CRFs. No documents shall be transferred from the site or destroyed without first notifying the Sponsor.

## 10.2.1 Case Report Forms (CRFs)

CRFs for individual subjects will be provided by the Sponsor or designee. CRFs must be legible and complete. CRFs for this study will be maintained in a study binder and data recorded on 2-part NCR paper. One copy will be kept by the investigator and the other copy will be collected by the study monitor. All forms should be completed using a black ballpoint pen. Errors should be lined out, *but not obliterated*, and the correction inserted, initialed, and dated by designated study personnel. Further data corrections will be performed on special "data correction forms" (DCFs) that will be provided to the investigator in case of erroneous or unclear data. The investigator will make the correction on the DCF and sign the DCF. The original will be sent to the study monitor and a copy retained with the CRFs.

A CRF must be completed and signed by the investigator for each subject enrolled, including those withdrawn from the study for any reason. The reason for withdrawal must be noted on a subject's study termination form.

CRFs must be kept current to reflect the subject's status at each phase during the course of the study. Subjects are not to be identified on CRFs by name; appropriately coded identification and the subject's initials must be used. The investigator must keep a separate log of the subjects' names and addresses.

Source documents such as the clinic chart are to be maintained separately from the CRF to allow data verification. Because of the potential for errors, inaccuracies, and illegibility in transcribing data onto CRFs, originals of laboratory and other test results must be kept on file with the subject's CRF. CRFs, source documents, and copies of test results must be available at all times for inspection by the study monitor. The following should also be available for review:

- Subject Screening Log, which should reflect the reason any subject screened for the study was found to be ineligible
- Delegation of Authority Log, which will list all site personnel with their responsibilities as delegated by the PI and their signatures. This log will be maintained at the site throughout the study
- Monitoring Log, which will list the date and purpose of all monitoring visits by the Sponsor or designee
- Enrollment Log, which will list subject initials and start and end dates for all enrolled subjects
- Product Inventory/Packing Slip, which will list the total amount of study device shipped to the site and received and signed for by the investigator
- Study Device Dispensing Log, which will list the lot number and total amount of study device used for each subject
- ICF, which must be available for each subject and be verified for proper documentation
- All correspondence

#### 10.2.2 Primary Source Documents

The investigator must maintain primary source documents supporting significant data for each subject's medical notes. These documents, which are considered "source data," should include documentation of:

- Demographic information
- Evidence supporting the indication for which the subject is being studied
- General information supporting the subject's participation in the study
- General history and physical findings
- Hospitalization or Emergency Room records (if applicable)
- Each study visit by date, including any relevant findings/notes by the investigator(s), occurrence (or lack) of AEs, and changes in medication usage
- Any additional visits during the study
- Any relevant telephone conversations with the subject regarding the study or possible AEs
- An original, signed ICF for study participation

The investigator must also retain all subject-specific printouts/reports of tests and procedures performed as a requirement of the study. During monitoring visits the monitor will validate CRF entries against these data sources.

